## **5.2. Informed Consent**

Study sites will obtain IRB/EC approval for this study.

An IRB/EC waiver of informed consent for study participation should be requested for those subjects who meet eligibility criteria and have retrospectively completed a 2-year postoperative visit, are deceased, or are lost to follow-up, per IRB/EC policy. If allowed, a retrospective data set will be collected on these subjects. A copy of the waiver of informed consent will be placed in the subject file.

Subjects who meet eligibility criteria, are alive, and have not completed a 2-year postoperative visit, will be contacted and asked to provide Informed Consent prior to any retrospective or prospective data collection. These subjects may consent for participation only in the retrospective phase of the study or may consent for participation in both the retrospective and prospective phases of the study. The informed consent process will be documented in the subject's medical record and on the study Case Report Forms (CRFs). The informed consent form (ICF) will be placed in the subject file and a copy will be provided to the subject.

If a subject refuses participation, no further information will be collected. Reason for exclusion should be noted on the Screening and Enrollment Log.

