## **8. SAFETY REPORTING**

Adverse Events (AE) related to the study device (Navio), the unicondylar implant, or procedure including Adverse Device Effects (ADE), Serious Adverse Device Effects (SADE), Unanticipated Serious Adverse Device Effect (USADE), and Device Deficiencies (DevD) occurring from the time of the study procedure until revision or study completion must be recorded on the appropriate CRF and reported. If the event is known to have been previously reported to Smith & Nephew, this must be noted on the CRF. After consent, in addition to all events related to Navio, the unicondylar implant or the procedure, all serious adverse events (SAE), regardless of causality, must be recorded on the appropriate CRF and reported to sponsor and IRB if necessary. Events leading to a revision should be reported at all times regardless of causality.

Adverse Device Effects (ADE) occurring after study completion will be handled as product complaints reportable by the Sponsor and will not be entered into the study database.

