#### **8.2. Safety: Investigator's Responsibilities**

##### Reporting of adverse events during the retrospective data collection portion of the study:

Investigators are responsible for documenting ADE, SADE, U(S)ADE and DevD identified during the medical record review. This includes events related to the study device (Navio), the unicondylar implant, or procedure. Investigators will record ADE, SADE, U(S)ADE and observed DevD, together with an assessment in the subject's source data. Investigators are responsible for documenting ADE, SADE, U(S)ADE and DevD on the appropriate CRF and submitting them to the Sponsor according to the timelines described.

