##### Reporting of adverse events during the prospective data collection portion of the study:

At each prospective contact with the subject, the Investigator must seek information on previous events and current events that could be deemed serious by specific questioning and, as appropriate, by assessment of the subject. All study device (Navio), unicondylar implant, and procedure related adverse events and all serious adverse events (SAE) regardless of causality, must be recorded on the appropriate CRF and reported to sponsor and IRB. Unresolved AE should be followed by the Investigator until the events are resolved or through to the end of the study, whichever occurs first. Unresolved AEs at the end of the subject's participation should be monitored by the Investigator as part of the site's normal standard of care.

All events must be recorded in standard English medical terminology.

The Investigator will categorize AE as mild, moderate or severe based on the following definitions:

- Mild: the subject is aware of the sign or symptom, but finds it easily tolerated. The event is of little concern to the subject and/or little clinical significance. The event is not expected to have any effect on the subject's overall health or well-being.
- Moderate: the subject has discomfort enough to cause interference with or change in usual activities. The event is of some concern to the subject's health or wellbeing and may require medical intervention and/or close follow-up.
- Severe: the adverse event interferes considerably with the subject's usual activities. The event is of definite concern to the subject and/or poses a substantial risk to the subject's health or wellbeing. The event is likely to require medical intervention and/or close follow-up and may be incapacitating or life threatening. Hospitalization and treatment may be required.

The Investigator is responsible for describing the relationship of the AE to the study device/procedure based on the following definitions:

- Unrelated: the event is clearly not related to the study device or procedure
- Possible: the event may or may not be related to the study device or procedure. A relationship cannot be ruled out.
- Definite: the event is clearly related to the study device or procedure.

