5.4 Safety Endpoints

Safety endpoints are as follows:

- Incidence of AEs,
- Incidence of AEs by severity,
- Incidence of AEs by relationship to knee implant (study device),
- Incidence of AEs by relationship to NAVIO System,
- Incidence of AEs that led to discontinuation,
- Incidence of AEs by outcome,
- Incidence of serious adverse events (SAEs),
- Incidence of adverse device effects (ADE),
- Incidence of serious adverse device effects (SADEs),
- Incidence of unanticipated adverse device effects (UADEs),
- AEs of special interest,
- Listing of revisions and details of components removed during revision.

6. Statistical Considerations

CONFIDENTIAL AND PROPRIETARY

This document contains information that is confidential and proprietary to Smith & Nephew PLC and Smith & Nephew, Inc. and is intended for use only by Smith & Nephew and its manufacturer. It shall not be reproduced or copied in whole or in part, nor shall the contents be disclosed by any means without prior written permission from Smith & Nephew, nor shall anyone make any use of it that is contrary to the expressed or implied wishes of Smith & Nephew.

Statistical Analysis Plan	 smith&nephew
A Retrospective Study of the NAVIO Robotic-assisted Surgical System	Number: 16-NPFS-11
	Version: Final 1.0, Jan 29, 2018
	Page: 12 of 25

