7.13 Analysis of Safety Endpoints

CONFIDENTIAL AND PROPRIETARY

This document contains information that is confidential and proprietary to Smith & Nephew PLC and Smith & Nephew, Inc. and is intended for use only by Smith & Nephew and its manufacturer. It shall not be reproduced or copied in whole or in part, nor shall the contents be disclosed by any means without prior written permission from Smith & Nephew, nor shall anyone make any use of it that is contrary to the expressed or implied wishes of Smith & Nephew.

Statistical Analysis Plan	 smith&nephew
A Retrospective Study of the NAVIO Robotic-assisted Surgical System	Number: 16-NPFS-11
	Version: Final 1.0, Jan 29, 2018
	Page: 23 of 25

- An overall summary AE table that would summarize as number (n) and percentages (%), the overall incidence according to subjects with at least one AE; subjects with at least one AE by worst severity (mild, moderate, or severe); subjects with at least one AE by worst outcome; subjects with an AE that led to study discontinuation; subjects with at least one AE by worst relatedness to investigational device; subjects with AEs by worst relationship to the NAVIO device; SAEs; ADEs; SADEs; UADEs and; AEs of special interest would be summarized. A Smith and Nephew Adverse Event Monitoring Board (AEMB) may be convened to review the list of and subsequently classify AEs into special interest AEs for additional AE summaries.
- Tables that summarize the incidence of AEs (each based on criteria previously specified in the overall summary table) would be generated. Each table would include the numbers (n) and percentages (%) of subjects with each AE as well as the cumulative events/episodes per AE.

All summaries and listings for the safety endpoints would use the safety population as the analysis population.

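### SAEs unrelated to the device, implant or procedure are collected only after consent, but SAP 7.13 divides them by the whole Safety Population

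*SAP*

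**What the plan says.** **Collection.** Protocol 8 sets two rules. From the procedure onward, events related to Navio, the implant or the procedure are recorded. SAEs of any cause are added only later: "After consent, in addition to all events related to Navio, the unicondylar implant or the procedure, all serious adverse events (SAE), regardless of causality". Protocol 8.2 repeats the split by phase. For record review, "Investigators are responsible for documenting ADE, SADE, U(S)ADE and DevD identified during the medical record review". At prospective contacts, all SAEs regardless of cause are recorded, and "the Investigator must seek information on previous events and current events that could be deemed serious by specific questioning". Protocol 8.3 also ties SAE reporting to the prospective portion. One exception covers every phase: "Events leading to a revision should be reported at all times regardless of causality".

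**Who has no post-consent period.** Protocol 5.2 and 10.3 allow a consent waiver, subject to IRB/EC policy, for eligible subjects who "have retrospectively completed a 2-year postoperative visit, are deceased, or are lost to follow-up". Only a retrospective data set is collected for them.

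**Denominator.** Protocol 9.3 and SAP 7.2 define the Safety Population as all who received the device, with no condition on consent or phase. SAP 5.4 lists SAE incidence separately from SADE incidence. SAP 7.13 reports both as n and %, and adds: "All summaries and listings for the safety endpoints would use the safety population as the analysis population". Neither document gives a separate N for subjects under all-cause collection, a split by phase, or an adjustment for observation time.

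**The concern.** A percentage is interpretable only if everyone in the denominator could have been counted in the numerator. For unrelated SAEs that do not lead to revision, this fails for waiver subjects. They are counted below the line, but no rule asks the site to record such an event for them.

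Death shows the problem most clearly. Under Protocol 8.1 B, an event that led to death is an SAE. A deceased subject may be enrolled under the waiver. If the death was unrelated, it will appear in the accountability report (Protocol 9.2, SAP 7.6), but the record-review rule does not require it in the SAE row. The study report could then disagree with itself.

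The overall AE rows share the problem. Protocol 8.1 A counts serious worsening of a previously recorded condition as an AE only during the prospective period, so those rows also mix two collection rules.

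Two-year safety is a stated objective (Protocol 2, SAP 4.1). A reader would take the SAE row as all-cause and covering all treated subjects, and would see a figure that is too low.

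**Working it through.** **The plan's own figures.** The documents state no SAE percentage, expected SAE risk or consented share, so there is no SAE figure to reproduce. The only number taken from the plan is the enrolled total in Protocol 9.1: 115 / (1 − 0.10) = 127.8, rounded up to 128. It serves here only as a denominator.

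**Definitions.**

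- R: share of subjects with an SAE that is related, or that leads to revision. These are collected in everyone.
- U: share, among subjects under all-cause collection and over their own collection window, whose only SAEs are unrelated and do not lead to revision.
- f: share of the Safety Population under all-cause collection.

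**Identity.** With R the same in both groups and no overlap between R and U:

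- reported SAE % = R + f × U
- SAE % among subjects under all-cause collection = R + U
- shortfall = (1 − f) × U

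The shortfall is zero if f = 100% or U = 0, and otherwise always downward.

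**Numbers (assumed: R = 3%, U = 10%, N = 128).**

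- f = 25% (32 subjects): 0.03 × 128 + 0.10 × 32 = 3.84 + 3.20 = 7.04; 7.04 / 128 = 5.5%
- f = 50% (64 subjects): 3.84 + 6.40 = 10.24; 10.24 / 128 = 8.0%
- f = 75% (96 subjects): 3.84 + 9.60 = 13.44; 13.44 / 128 = 10.5%
- f = 100%: 3.84 + 12.80 = 16.64; 16.64 / 128 = 13.0%

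**Range over U, with R = 3%.**

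| U | f = 25% | f = 50% | f = 75% | no dilution |
|---|---|---|---|---|
| 5% | 4.25% | 5.5% | 6.75% | 8% |
| 10% | 5.5% | 8.0% | 10.5% | 13% |
| 20% | 8.0% | 13.0% | 18.0% | 23% |

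**Rows not affected.** ADEs, SADEs and revisions fall under R and are sought in every subject, so the full Safety Population suits them.

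**The case against.** The strongest reply is that little of the safety reporting is touched. Related serious events, revisions and events leading to revision are collected for everyone. The Protocol synopsis describes the safety assessment in terms of device- and procedure-related events, and SAP 7.13 shows ADEs, SADEs and AEs by relatedness separately. The SAE row is descriptive and carries no test. Waivers depend on IRB/EC policy, so f could be close to 100%.

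Most of this stands as a limit on scope. It does not remove the mismatch, because SAP 5.4 names SAE incidence as an endpoint in its own right. The waiver is also a planned route: Protocol 5.1 screens from each investigator's first Navio case, and Protocol 6.3 has completed 2-year visits collected retrospectively.

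Three stronger readings are tempting, and the documents do not support them.

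- A reader might infer that SAEs are not collected at all in waiver subjects, so that the reported figure is the true figure times f. For the 13% example this would give 3.25%, 6.5% and 9.75%. It ignores R, which is collected in everyone; the correct values are 5.5%, 8.0% and 10.5%.
- A reader might infer that subjects who consent only to the retrospective phase cannot contribute an unrelated SAE. Protocol 8 starts all-cause collection at consent, whereas 8.2 and 8.3 start it with the prospective portion. Their status is unclear.
- A reader might infer that consented subjects are covered only from consent onward. Protocol 8.2 also asks about previous events at prospective contacts, without saying whether SAEs before consent are counted.

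**Conclusion.** The point holds in a limited form. Where waiver subjects are enrolled and unrelated SAEs occur, the SAP as written understates the unrelated part of the SAE percentage, and of the overall AE rows, by a factor f. In the illustration, 13% appears as 5.5%, 8.0% or 10.5%. The direction follows from the documents. The size does not, since f, R and U are all assumed, with no overlap and the same R in both groups.

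An all-cause percentage confined to subjects under all-cause collection would still not be a 2-year incidence, because their observation window varies and its start is not settled. The sample size and the primary non-inferiority test are untouched. This is worth correcting before the tables are produced, but it concerns descriptive rows only.

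**What to change.** In SAP 7.13, for both the overall summary table and the separate SAE incidence table:

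1. Report all-cause SAEs with subjects under all-cause collection as the denominator. Give their N and observation period, and state that this is not a 2-year incidence.
2. Keep related AEs, ADEs, SADEs and revisions on the full Safety Population.
3. Split the overall AE row by collection phase. Labelling it as related events only would be inaccurate, because unrelated SAEs after consent and unrelated events leading to revision also enter it.
4. Reconcile Protocol 8 with 8.2 and 8.3: state whether subjects consenting only to the retrospective phase are under all-cause collection, and whether SAEs before consent count.

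The cost is SAP wording, changed denominators in the affected tables and a clarification of the collection rule. Items 1 to 3 use data already planned. The downside is that the SAE percentage will be higher and rest on fewer subjects: 32 of 128 if f were 25%.

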7.14 Other Data Summaries

- The type of analysis carried out on the primary endpoint, the Kaplan-Meier estimates would be summarized non-inferentially for the following subgroups using the safety population:
 - Age (< 60 years versus \geq 60 years),
 - BMI (< 30 kg/m² versus \geq 30 kg/m²)

CONFIDENTIAL AND PROPRIETARY

This document contains information that is confidential and proprietary to Smith & Nephew PLC and Smith & Nephew, Inc. and is intended for use only by Smith & Nephew and its manufacturer. It shall not be reproduced or copied in whole or in part, nor shall the contents be disclosed by any means without prior written permission from Smith & Nephew, nor shall anyone make any use of it that is contrary to the expressed or implied wishes of Smith & Nephew.

Statistical Analysis Plan	 smith&nephew
A Retrospective Study of the NAVIO Robotic-assisted Surgical System	Number: 16-NPFS-11
	Version: Final 1.0, Jan 29, 2018
	Page: 24 of 25

- Sex (males versus females), and
- Region (Europe versus USA).

For the subgroup analysis by region, investigational sites within Europe would be pooled into one virtual site and all investigational sites within the USA would be pooled into another virtual site.

- Other data summaries that would be performed using the safety population, are as follows:
 - Shift from baseline to 2 years (24 months) in overall physical health,
 - Shift from baseline to 2 years (24 months) in overall emotional problems.
- Subject discharge data would be summarized descriptively using the safety population for length of hospital stay prior to discharge (days) as a continuous variable and using categorical summary statistics (n and %) for place discharged to and primary ambulatory support prior to discharge.
- Listing of medical history.
- Summary of KSS and VR-12 derived endpoints at 6 months, 12 months, 18 months, 30 months and 36 months.

7.15 Changes in Analysis Methods Specified in the Protocol

- The safety population and the full analysis set (FAS) population as defined in the protocol are exactly the same. As a result thus, in this SAP, there was no further reference to the FAS population.
- The change from baseline to 24 month endpoints for KSS and VR-12 has been modified to be the summary characteristics for the endpoints at 24 months.

CONFIDENTIAL AND PROPRIETARY

This document contains information that is confidential and proprietary to Smith & Nephew PLC and Smith & Nephew, Inc. and is intended for use only by Smith & Nephew and its manufacturer. It shall not be reproduced or copied in whole or in part, nor shall the contents be disclosed by any means without prior written permission from Smith & Nephew, nor shall anyone make any use of it that is contrary to the expressed or implied wishes of Smith & Nephew.

Statistical Analysis Plan	 smith&nephew
A Retrospective Study of the NAVIO Robotic-assisted Surgical System	Number: 16-NPFS-11
	Version: Final 1.0, Jan 29, 2018
	Page: 25 of 25

These modifications were implemented because all 27 subjects analyzed for the interim analyses had missing baseline KSS and VR-12 data.

8. References

1. Australian Orthopaedic Association National Joint Replacement Registry. Annual Report. Adelaide: AOA; 2015.

CONFIDENTIAL AND PROPRIETARY

This document contains information that is confidential and proprietary to Smith & Nephew PLC and Smith & Nephew, Inc. and is intended for use only by Smith & Nephew and its manufacturer. It shall not be reproduced or copied in whole or in part, nor shall the contents be disclosed by any means without prior written permission from Smith & Nephew, nor shall anyone make any use of it that is contrary to the expressed or implied wishes of Smith & Nephew.

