## 2. STUDY OBJECTIVES

This clinical study will evaluate the 2-year safety and effectiveness of the Navio System in UKR in subjects  $\geq$  18years of age, as demonstrated by revision rate, changes in clinical, functional, and quality of life outcomes over time, radiographic assessments and Adverse Event (AE) incidence and frequency.

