## 2.2. Secondary Endpoints

Given the retrospective-prospective study design, secondary endpoint data will be collected to the extent that it is available and will include:

- Change in Knee Society Score (KSS) from baseline to 2 years (-3months) or greater postoperative
- Change in VR12 from baseline to 2 years (-3months) or greater postoperative
- Anterior/Posterior and lateral radiographic assessments:
  - Radiographic findings
  - Component orientation
  - Radiolucencies
  - Migration
  - Osteolysis
  - Stress shielding
  - Subsidence

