6.1 Determination of Sample Size

The sample size obtained for study is based on the non-inferiority of the percent of revision-free survival expected to be obtained at 2 years in the study, π to one obtained from existing literature, π_0 . The Australian Orthopaedic Association National Joint Replacement Registry 2015 Annual Report (1) indicates that the revision-free survival at 2-years is 95.7%.

Using a non-inferiority margin, δ of 7%, a sample size of 115 subjects would provide at least 80% power at the 5% significance level using the exact binomial method. To allow for a 10% attrition and drop-out rate, a total of approximately 128 subjects would be enrolled into the study.

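### SAP 7.15 drops change from baseline in KSS and VR-12 for the whole study on the evidence of 27 subjects, with no fallback for any others who have both values

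*SAP*

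**What the plan says.** Protocol section 2 includes among its measures of safety and effectiveness "changes in clinical, functional, and quality of life outcomes over time". Protocol 2.2 turns this into two score-based secondary endpoints: "Change in Knee Society Score (KSS) from baseline to 2 years (-3months) or greater postoperative" and "Change in VR12 from baseline to 2 years (-3months) or greater postoperative". The same section makes the data conditional on the records: "secondary endpoint data will be collected to the extent that it is available". Protocol 6.2 and the schedule tables in both documents still have pre-operative KSS and VR-12 collected.

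SAP 7.15 says that the change-from-baseline endpoint "has been modified to be the summary characteristics for the endpoints at 24 months". The reason given is that "all 27 subjects analyzed for the interim analyses had missing baseline KSS and VR-12 data". SAP 5.2 and 7.11 follow this. KSS and VR-12 are summarised descriptively at 24 months, as observed cases without imputation. SAP 7.14 adds the same kind of summary at 6, 12, 18, 30 and 36 months. Neither score is among the baseline variables in SAP 7.5.

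SAP 7.14 nevertheless keeps "Shift from baseline to 2 years (24 months) in overall physical health", and a matching shift for emotional problems, both in the safety population.

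**The concern.** The reason in SAP 7.15 describes 27 subjects, but the rule it supports applies to all of about 128. If any of the others has both a pre-operative and a follow-up score, the SAP as written collects the pair and then leaves it out of every planned summary of change. A postoperative score alone describes the level reached. It does not show how far the subject moved from the pre-operative state, which is what the protocol endpoint asks.

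Two further consequences follow. No summary table named in the SAP would show how many subjects have a baseline KSS or VR-12, so a reader of the report could not check the reason given for the change. And SAP 7.14 still relies on some baseline measure of physical and emotional health, without saying whether it is the measure that SAP 7.15 treats as missing.

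**Working it through.** **Inputs**
- Planned enrolment: about 128 (SAP 6.1, "a total of approximately 128 subjects would be enrolled into the study"). This reproduces: 115 / (1 − 0.10) = 127.8, rounded up to 128.
- Subjects behind the change: 27, none with a baseline KSS or VR-12 (SAP 7.15).
- Number of the remaining subjects with a baseline: not given in either document.
- SD of the change: not given, so precision is expressed in SD units.

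**Share of the study behind the decision**
- 27 / 128 = 0.211, or 21%.
- 128 − 27 = 101 subjects about whom SAP 7.15 says nothing.

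**What 0 of 27 implies for the rest, if the 27 are representative (assumption)**
- Exact one-sided 95% upper bound on availability: 1 − 0.05^(1/27) = 0.105, or 10.5%. Then 0.105 × 101 = 10.6, about 11 subjects.
- Upper limit of the two-sided 95% interval: 1 − 0.025^(1/27) = 0.128, or 12.8%. Then 0.128 × 101 = 12.9, about 13 subjects.

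**If they are not representative**

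The SAP does not say how the 27 were chosen. SAP 6.3 marks interim analysis as not applicable, so nothing there helps. Up to 10 sites contribute, and baseline scores come from each site's medical records. If recording practice differs by site (assumption), 0 of 27 says little about other sites, and the count among the remaining subjects can lie anywhere from 0 to 101.

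**Precision of a paired mean change**

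The 95% CI half-width in SDs of the change is t(0.975, n − 1) / √n.

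| Pairs | Half-width (SD) | Case |
|---|---|---|
| 11 | 2.228 / √11 = 0.67 | one-sided bound |
| 13 | 0.60 | two-sided upper limit |
| 50 | 0.28 | possible only if the 27 are not representative |
| 101 | 0.20 | ceiling |

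These counts assume that every subject with a baseline also has a follow-up score. Incomplete follow-up would lower them.

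**SAP sections side by side**
- 7.15 removes change from baseline for KSS and VR-12.
- 7.11 analyses secondary endpoints as observed cases. A paired summary limited to subjects with both values fits that rule and needs no new method.
- 7.14 keeps two shifts from baseline to 24 months. Their labels do not match any VR-12 sub-domain in SAP Table 4 or SAP 5.2, and no source is named. If they come from the pre-operative VR-12, they face the same gap as 7.15. If they come from elsewhere, the SAP should say where.
- Neither shift item is labelled as a KSS measure, so no KSS comparison with baseline is planned anywhere.

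**The case against.** The strongest defence is that the protocol foresaw this. It promised secondary data only as far as the records allow. Protocol 9.4 permits plain summary statistics where further analysis is not warranted or appropriate, and Protocol 9.2 leaves missing-data methods to the SAP. The SAP discloses the change and its reason in the proper section. Every subject examined lacked a baseline, so the sponsor had grounds to expect few pairs. A handful of pairs from one or two sites could mislead, the endpoints are descriptive and unpowered, and the primary analysis is untouched.

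Most of this stands as a reason for restraint. It does not justify removing the summary for a subject who has both values. The availability clause limits what is collected, and the clause in Protocol 9.4 concerns cases where analysis is unsuitable. Neither has been shown to apply to the 101 subjects not described.

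Three stronger readings are tempting, and the documents do not support them:
- A reader might infer that the trial cannot report improvement. Pre-operative scores are still collected where available and SAP 7.14 keeps two shift summaries, so paired change in KSS and VR-12 is unplanned rather than impossible.
- A reader might infer that known paired data are being discarded. No document reports a single subject with a baseline.
- A reader might infer that SAP 7.14 and 7.15 contradict each other. Because the source of the shift items is not stated, what is shown is an undefined variable that needs reconciling with 7.15.

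Nor does the whole objective go unanswered: revision, radiographic findings, adverse events and the postoperative course of both scores are still reported.

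**Conclusion.** The point holds as a cheap improvement. On the evidence of 27 subjects, 21% of planned enrolment, SAP 7.15 withdraws two protocol endpoints for the whole study and makes no provision for others who may have paired values. What is lost is unknown. It is at most about 11 pairs (half-width about 0.67 SD) if the 27 are representative, and between 0 and 101 if availability varies by site. Both are assumptions, because the documents give neither the number of baselines nor how the 27 were selected. For KSS the plan leaves no comparison with baseline. The source of the two SAP 7.14 shift items is undefined. The primary endpoint, its sample size and its test are not affected.

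**What to change.** - Keep the 24-month summaries as they are.
- Report the number of subjects with a baseline KSS and with a baseline VR-12.
- Where both values exist, add an observed-case paired summary of change in KSS and in VR-12 PCS and MCS: number of pairs, mean change and 95% CI. Use the same follow-up value as the 24-month summary, and label the result descriptive and possibly selective.
- In SAP 7.14, name the instrument and item behind each shift summary.
- Align SAP 5.2, 7.11, 7.14 and 7.15 with these changes.

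The cost is SAP wording and one table, with no new data. The downside is that the paired subset may be small, selective or empty. If it is empty, the table documents the reason for the sponsor's change. If it is not, the protocol endpoint is reported under a rule set in advance.
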